11.1.1 BIS™ Sensor Risks

The BIS™ Sensor is applied directly to the patient's skin to enable recordings of electrophysiological (such as EEG) signals. The sensor will be used as per IFU. The sensors used in this study may expose subjects to the following risks:

- Minor discomfort, allergic reaction, or skin irritation (such as redness, itching) at the sensor application site is probable but is usually self-limited within hours.
- Pressure points/ injury in application areas are possible but anticipated to be rare due to the short duration of the study. Care in the application and removal of the sensors is advised. Skin reactions will be observed during and after the study procedures.
- Electric shock is very rare, and the product design and testing ensure insulation and ground fault detection.
- Burn to the skin (due to a small amount of heat generated) is a rare unanticipated risk, and not likely due to the short duration of the study.

For more information on Sensor warnings and cautions, refer to Sensor IFU.

11.1.2 BIS™ Monitoring System Risks

BIS™ Monitoring System will be used per IFU. For more information on warnings and cautions, refer to IFU.

Medtronic Business Restricted

11.1.3 Pulse and Tissue Oximetry Sensor

Pulse and Tissue Oximetry Sensor placement involves positioning pulse and tissue oximetry sensors on the subject per the IFUs.

The sensors may be warm to the touch. Under normal operating conditions (no fault conditions), the sensors are not expected to overheat. If the sensors are too warm, they will be removed immediately.

The sensors exert a minimal amount of pressure. Sensors may leave minor impressions at the sensor application site, which should fade and resolve within the day. They should not cause discomfort. If the sensors are too uncomfortable, they will be removed.

Adhesive sensors may cause some irritations to the skin in some subjects. Typical skin irritations present with redness of the skin, and in some cases of sensitivity, an allergic reaction can occur. Removal of the sensor may cause pulling of the skin or hair, and this can be felt as pain. The risk in the use of oximetry sensors is believed to be minimal.

A heating pad or hot water bottles may be used on the hands to improve circulation. The subject may experience some mild discomfort if the water is too warm. To minimize the discomfort, the subject will be asked if the heating is too warm, it will be turned on the lowest level possible for comfort, removed or additional separation will be used between the heater and the site for comfort.

11.1.4 General Anesthetics

There are some risks associated with taking general anesthetics, but they are relatively safe when administered correctly. General anesthesia will be administered per institutional guidance. All Subjects will be monitored by health care professionals closely for the effects. The most common side effects of general anesthesia include sore throat due to the breathing tube, nausea, vomiting, dizziness, bruising, or soreness from the IV drip, shivering and feeling cold, difficulty passing urine. These may occur despite the best efforts to avoid them.

Also, when placing a breathing tube, there is a small risk that the anesthesia provider can damage the subject's teeth. This risk increases if the subject has loose teeth or other dental problems. With any medication given, the Subject could have an allergic reaction. Although rare, unexpected severe complications with anesthesia can occur and include, but not limited to, the remote possibility of infection, bleeding, drug reactions, blood clots, loss of sensation, loss of limb function, paralysis, stroke, brain damage, heart attack or death. The anesthesiologist will be present to minimize all risks related to anesthesia.

11.2. Potential Benefits

There are no medical benefits to the subjects who participate in this study. There is, however, the potential for benefiting future subjects should this study enable the development of improved medical monitoring devices.

11.3. Risk-Benefit Rationale

Medtronic has determined that this is a study of a “non-significant risk device” due to the nature of the devices being tested. Utilizing the FDA criteria^{1,2} listed below to distinguish between significant and non-significant risk devices, Medtronic has determined that:

- The device under investigation is not intended as an implant and does not present a potential for serious risk to the health, safety, or welfare of a subject;
- The device under investigation is not purported or represented to be for use supporting or sustaining human life and does not present a potential for serious risk to the health, safety, or welfare of a subject;
- The device under investigation is not for the use of substantial importance in diagnosing, curing, mitigating, or treating disease, or otherwise preventing impairment of human health, and does not present a potential for serious risk to the health, safety, or welfare of a subject; and
- The device under investigation does not otherwise present a potential for serious risk to the health, safety, or welfare of a subject.

The potential risks of these devices have been assessed and are not greater than those of currently approved and marketed devices of the same type (e.g., pulse and tissue oximeters, EtCO₂ monitors, non-invasive blood pressure monitors, ECG or respiration monitors). Society may benefit from more accurate medical monitors.

Medtronic requests that the reviewing IRB indicates its agreement with this determination of non-significant risk device in its letter of approval for this study.

11.4. Risk Determination

Medtronic has determined that this is a study of “non-significant risk”.

¹ 21CFR812.2 (b)(1)(ii) and 21CFR812.3(m)

² Information Sheet Guidance For IRB/EC , Clinical Investigators, and Sponsor. Significant Risk and Non-significant Risk Medical Device Studies/January 2006/UMC126418

12. Adverse Events and Device Deficiencies

12.1 Adverse Events

AE definitions are provided in Table 6.

AE information will be collected throughout the study from the enrollment through study exit.

A list of anticipated adverse events and risks that are expected in nature is included in Section 10.

Reporting of these events to Medtronic will occur via prompt email and the AE eCRF. Each event must be reported separately. Documented pre-existing conditions are not considered AEs unless the nature or severity of the condition has worsened.

For AEs that require immediate reporting (see Table 7), initial reporting must be done by email, phone, , and then on the eCRF completing as much information as possible. The completed AE eCRF must be submitted to Medtronic as soon as possible.

Any medication/treatment associated with the treatment of an AE must be reported

All AEs considered at least possibly related to the study will be followed until resolved, stabilized, and/or returned to baseline.

Medtronic will immediately conduct an evaluation of reported events. Table 5 shows event reporting requirements. At a minimum, the following information will be recorded:

- A description of the event
- The date of event onset
- The relatedness of the event to the device
- Actions are taken as a result of the event
- The outcome of the event

Table 5: Definition of Adverse Events and Device Deficiencies

General	
Adverse Event (AE)	
Any untoward medical occurrence, unintended disease or injury, or untoward clinical signs (including abnormal laboratory findings) in subjects, users or other persons, whether or not related to the investigational medical device.
 
NOTE 1: This definition includes events related to the investigational medical device or the comparator.
 
NOTE 2: This definition includes events related to the procedures involved.

Medtronic Business Restricted

	
NOTE 3: For users or other persons, this definition is restricted to events related to investigational medical devices.

Adverse Device Effect (ADE)	
Adverse event related to the use of an investigational medical device.
 
NOTE 1: This definition includes adverse events resulting from insufficient or inadequate instructions for use, deployment, implantation, installation, or operation, or any malfunction of the investigational medical device.
 
NOTE 2: This definition includes any event resulting from use error or from intentional misuse of the investigational medical device.

Device Deficiency (DD)	
Inadequacy of a medical device with respect to its identity, quality, durability, reliability, safety or performance.
 
NOTE: Device deficiencies include malfunctions, use errors, and inadequate labeling.

Relatedness	
Device Related	An AE that results from the presence or performance (intended or otherwise) of the device.
Procedure Related	An AE that occurs related to the procedure.
Seriousness	
Serious Adverse Device Effect (SADE)	Adverse device effect that has resulted in any of the consequences characteristic of a Serious Adverse Event.
Serious Adverse Event (SAE)	
An adverse event that
 
a) led to death,b) led to serious deterioration in the health of the subject, that either resulted in
1) a life-threatening illness or injury, or2) a permanent impairment of a body structure or a body function, or3) in-subject or prolonged hospitalization, or4) medical or surgical intervention to prevent life-threatening illness or injury or permanent impairment to a body structure or a body function,c) led to fetal distress, fetal death or a congenital abnormality or birth defect. 
NOTE: Planned hospitalization for a pre-existing condition, or a procedure required by the CIP, without serious deterioration in health, is not considered a serious adverse event.

Unanticipated Adverse Device Effect (UADE)	Any serious adverse effect on health or safety or any life-threatening problem or death caused by, or associated with, a device, if that effect, problem, or death was not previously identified in nature, severity, or degree of incidence in the CIP or application (including a supplementary plan or application), or any other unanticipated serious problem associated with a device that relates to the rights, safety or welfare of subjects.

Complication	
An adverse event that includes the following is considered a complication:
 
• Results in death,• Involves any termination of significant device function, or• Requires an invasive intervention 
Non-invasive (21 CFR 812.3 (k)): when applied to a diagnostic device or procedure, means one that does not by design or intention:
 
• Penetrate or pierce the skin or mucous membranes of the body, the ocular cavity, or the urethra, or• Enter the ear beyond the external auditory canal, the nose beyond the nares, the mouth beyond the pharynx, the anal canal beyond the rectum, or the vagina beyond the cervical os 
Where "penetrate" means: to pass, extend, pierce, or diffuse into or through something; to enter by overcoming resistance; to gain entrance to, and "pierce" means to force a way into or through something
 
NOTE (FDA): Blood sampling that involves simple venipuncture is considered noninvasive, and the use of surplus samples of body fluids or tissues that are left over from samples taken for non-investigational purposes is also considered noninvasive.

Observation	
Any AE that is not a complication.
 
NOTE 1: Only system or procedure related AEs will be classified as "Complication" or "Observation"

12.2.1 Adverse Event and Device Deficiency Classification

All AE and DD will be reviewed by a Medtronic representative. AEs will be classified according to the definitions provided.

Upon receipt of AE at Medtronic, a Medtronic representative will review the AE/DD for completeness and accuracy and when necessary will request clarification and/or additional information from the Investigator. Medtronic will utilize MedDRA for Regulatory Activities, to assign a MedDRA term for each AE based on the information provided by the investigator.

Regulatory reporting of AEs and DDs will be completed according to local regulatory requirements. Refer to Table 5 for a list of required investigator and Medtronic reporting requirements and timeframes. It is the responsibility of both to abide by any additional AE reporting requirements stipulated by the EC responsible for oversight of the study.

For emergency contact regarding a UADE, USADE, SAE and/or SADE, contact a study representative immediately (refer to the study contact list provided in the study site's study documents binder/investigator site file or refer to the Sponsor contact information provided on the title page).

AEs and Deaths will be classified according to the standard definitions as outlined below:

Table 6: Adverse Event Classification Responsibilities

What is classified?	Who classifies?	Classification Parameters
Relatedness	Investigator	Device, Procedure
	Sponsor	Device, Procedure, BIS™ System components
Seriousness	Investigator	SAE, DD with SADE potential
	Sponsor	SAE, UADE/USADE, Complication or Observation (for all procedure related adverse events), DD with SADE potential
Diagnosis	Investigator	Based on presenting signs and symptoms and other supporting data
	Sponsor	MedDRA term assigned based on the data provided by Investigator

12.2.2 Adverse Event and Device Deficiency Reporting Requirements

Regulatory reporting of AEs and DDs will be recorded and reported according to local regulatory requirements. It is the responsibility of the Investigator and the sponsor to abide by the AE reporting requirements stipulated by local law and the study site's IRB.

Table 7: Reporting Requirements for Events

Serious Adverse Device Effects (SADE), including Unanticipated Adverse Device Effect (UADE):	
Investigator submits to:	
Medtronic	Within 24 hours after the investigator first learns of the event.
Regulatory Authority	As per local reporting requirements.
IRB	Submit to IRB per local reporting requirement.
Sponsor submits to:	
Regulatory Authorities	Reporting timeframe as per local requirement.
IRB	Submit to IRB per local reporting requirement.
Serious Adverse Events (SAE)	
Investigator submits to:	
Medtronic	Within 24 hours after the investigator first learns of the event.
Regulatory Authority	As per local reporting requirements.
IRB	Submit to IRB per local reporting requirement.
Sponsor submits to:	
Regulatory Authorities	Reporting timeframe as per local requirement.
IRB	Submit to IRB per local reporting requirement.
Adverse Device Effects (ADE)	
Investigator submits to:	
Medtronic	Within 24 hours after the investigator first learns of the event.
Sponsor submits to:	
Regulatory Authority	As per local reporting requirements.
IRB	Submit to IRB per local reporting requirement.
Sponsor submits to:	
Regulatory Authorities	Reporting timeframe as per local requirement
IRB	Submit to IRB per local reporting requirement.
All other AEs	
Investigator submits to:	
Medtronic	Submit as soon as possible, but no later than within 10 working days after the investigator first learns of the event.
Regulatory Authority	As per local reporting.
IRB	Submit to IRB per local reporting requirement.
Device Deficiency with SADE potential	
Investigator submits to:	
Medtronic	No later than 48 hours after the investigator first learns of the event.
Regulatory Authorities	As per local reporting requirements.
IRB	As per local reporting requirement.
Sponsor submits to:	
Regulatory Authorities	As per local reporting requirements.
IRB	As per local reporting requirement.
All other Device Deficiencies	
Investigator submits to	

Medtronic Business Restricted

Medtronic	No later than 48 hours after the investigator first learns of the event.
Regulatory Authorities	As per local reporting requirements.
IRB	As per local reporting requirement.
Sponsor submits to:	
Regulatory Authorities	As per local reporting requirements.
IRB	As per local reporting requirement.

12.3 Foreseeable AE or SAE

The information provided in this section pertains to foreseeable adverse events that may be observed in this study and may collectively assist in identifying those events for a given device or therapy that are unexpected in nature. The foreseeable adverse events information consists of two parts: 1) adverse events reported in published literature, and 2) additional foreseeable adverse events. Evaluation of potentially anticipated events, adverse device effects observed in previous clinical studies, and reported events in literature may be used in combination with device labeling, current event reporting information, and other published data to assess for an unexpected occurrence.

12.3.1 Surgical Procedure

The study will be collecting data during the SOC surgical procedure; therefore, standard adverse events associated with a surgical procedure may be experienced (e.g., anesthesia complications, injury, infections, bleeding, exacerbation of pre-existing conditions, healing complications, etc.). Data from peer-reviewed literature indicates that approximately 10% of the surgical patients had at least one AE related to the surgical procedures or the hospital environment [18] [19]. These events are not necessarily related to the study devices. In this study, the surgical procedure will be performed per SOC, and events related to the surgical procedure will not be captured.

All device and anesthesia management related to adverse events will be captured.

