10.6 Enrollment

A subject is considered enrolled when the consent process has been finalized. The date the subject (or the subject's authorized/designated representative or guardian) signed the IC and Data Protection Authorization, as required by law, must be documented in the subject's medical records. A log of all

Medtronic Business Restricted

subjects enrolled in the study should be maintained. Enrollment can be a stand-alone visit or can occur on the same day as the baseline visit. Once consent is obtained, report adverse events/deaths, study deviations and subject exits as they occur.

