10.11 Assessment of Safety

For safety analyses, adverse events will be summarized using frequency counts and percentages, refer to *Section 14*. Descriptive statistics will be provided by event type, severity, and relationship to study procedures and devices. Individual listings of adverse events, including event type, start date, duration, severity, and device-relatedness, will be provided as appropriate. Adverse events occurring during the procedure or 48 hours after the procedure will be recorded. For AEs and AE reporting requirements, refer to *Section 12*.

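### Protocol section 12.3.1 excludes surgery-related events from capture, contradicting the protocol's own AE definition and reporting rules; for events not listed in 12.3.2, whether a record exists can depend on a prior causality call

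*Protocol*

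**What the plan says.** Protocol 12.3.1 explains that ordinary surgical adverse events may occur, cites a literature figure of about 10% of surgical patients, and concludes that "the surgical procedure will be performed per SOC, and events related to the surgical procedure will not be captured". The next sentence keeps events related to the device and to anesthesia management in scope.

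Other sections of the protocol set a wider rule:

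- Section 12.1 defines an adverse event as "Any untoward medical occurrence, unintended disease or injury, or untoward clinical signs (including abnormal laboratory findings) in subjects, users or other persons", regardless of any relation to the device. A note adds: "This definition includes events related to the procedures involved". On timing it says: "AE information will be collected throughout the study from the enrollment through study exit".
- Section 10.6: "Once consent is obtained, report adverse events/deaths, study deviations and subject exits as they occur".
- Section 10.11: "Adverse events occurring during the procedure or 48 hours after the procedure will be recorded".
- Section 12.2.2 has investigators send SAEs to the sponsor "Within 24 hours after the investigator first learns of the event" and all other AEs within 10 working days. Neither row has a causality condition.
- Sections 12.1 and 12.2.1 make procedure-relatedness a class given to an event already reported. The sponsor's classification duties include "Complication or Observation (for all procedure related adverse events").

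Section 12.3.2 lists events to be captured during anesthesia and sets no condition on their cause. SAP 7.10 plans a summary of events by severity and relationship for each study group.

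**The concern.** Two current rules give opposite instructions for the same event. Under 12.1 and 12.2.2 the event is recorded and then classified. Under 12.3.1 it is classified first and, if judged surgical, not recorded. The boundary is also unclear: 12.3.1 names anesthesia complications and injury among its examples of surgical events, then says that anesthesia-management events are captured.

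Two things are at stake. The first is completeness. As written, 12.3.1 would let a site omit a serious surgical event or a death, yet section 10.13 counts late SAE reporting as a major deviation. Up to eight sites may settle the conflict differently. The second is comparability. The arms differ in how sevoflurane is titrated, so an event that looks surgical is not necessarily independent of allocation. If the attribution is made by someone who knows the arm, and made before recording, the AE summary by group may reflect attribution habits as well as event rates.

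**Working it through.** The main check sets the texts side by side. No power or alpha figure bears on this point, so there is no planned figure to reproduce.

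**Step 1. Is there a conflict?** Take a serious bleed during surgery that the investigator attributes wholly to the operation.

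- 12.3.1: not captured.
- 12.1: an adverse event under the basic definition, and inside the enrollment-to-exit window.
- 10.6: reportable, because consent has been given.
- 10.11: recorded, because it occurred during the procedure.
- 12.2.2: sent to the sponsor within 24 hours. If it were non-serious, within 10 working days.

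Both sets of instructions cannot be followed.

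**Step 2. Does it depend on the meaning of 'procedure'?** The note in 12.1 and the procedure-related class in 12.1 and 12.2.1 might mean study procedures only; 10.11 speaks of study procedures when it describes relatedness. Setting those texts aside leaves the basic AE definition and window in 12.1, plus 10.6, the recording rule in 10.11, and 12.2.2. The conflict remains.

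**Step 3. Which events are exposed?** Section 12.3.2 covers, during anesthesia, blood pressure and heart rate changes above 20% from baseline, cardiac arrest, laryngospasm, bronchospasm, desaturation, hypercarbia, and movement and similar signs. These are captured whatever their cause. Exposed events are those off the list or after anesthesia, such as injury, bleeding and infection.

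**Step 4. Who makes the call?** In the BIS arm sevoflurane is titrated to a displayed value; in the SP arm the value is concealed. The anesthesia team therefore knows the arm. The documents do not say who applies 12.3.1 or whether AE assessors are masked.

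**Step 5. Scale.** Inputs: about 10% of surgical patients with at least one AE related to surgery or the hospital environment (12.3.1); a minimum of 108 qualifying subjects, 18 per treatment group in each of 3 age groups (14.2), so 3 × 18 = 54 per arm.

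- Both arms: 0.10 × 108 = 10.8 subjects.
- Per arm: 0.10 × 54 = 5.4 subjects.
- If only half of those events were attributed to surgery (an assumption): 0.5 × 10.8 = 5.4 subjects in all, 2.7 per arm.

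**Step 6. How a distortion could arise (assumed shares, for illustration).** Let the true rate be 10% in both arms, and let the stated share be attributed to surgery and left unrecorded.

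| Share, SP | Share, BIS | Recorded, SP | Recorded, BIS |
|---|---|---|---|
| 50% | 50% | 54 × 0.10 × 0.5 = 2.7 | 54 × 0.10 × 0.5 = 2.7 |
| 30% | 70% | 54 × 0.10 × 0.7 = 3.8 | 54 × 0.10 × 0.3 = 1.6 |

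Equal attribution undercounts without creating an imbalance. Unequal attribution creates an apparent difference where none exists. The documents do not indicate which case would apply, or in which direction.

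**The case against.** The strongest reply is that 12.3.2 already protects the events most plausibly linked to anesthetic depth. That is right, and it limits the point. A reader might infer that movement and hemodynamic events are filtered out, or that nothing is recorded when a child moves and is injured. The documents do not support this. The movement is captured under 12.3.2 and again as part of the Clinical Anesthesia Assessment in both arms. A serious injury would still fall under the 24-hour rule in 12.2.2. Only the record of the injury itself is in doubt, because 12.3.1 and 12.2.2 disagree about it.

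Other replies stand in part:

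- The closing sentence of 12.3.1 can be read to keep events of mixed attribution in scope. It does not help with an event attributed to surgery alone.
- Monitors compare CRFs with source and check that AEs are reported (16.1.1), so an unrecorded event is not necessarily beyond recovery. But monitors then face the same two rules, and the sponsor's classification in 12.2.1 starts from events it has received.
- AEs are only summarized descriptively, and no test between arms is planned. That lowers the stakes but does not remove the contradiction.
- It would be going too far to say that causality is judged by unmasked assessors as a stated feature of the plan. That is an inference from the design.

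**Conclusion.** The contradiction is real and in current text. Section 12.3.1 cannot be reconciled as written with 10.6, 10.11, 12.1 and 12.2.2, and it makes no exception for serious events or deaths. Its practical reach is limited to events that 12.3.2 does not list, or that occur after anesthesia. For those, a record can depend on a causality call made before recording, which could distort the AE summary by group in SAP 7.10. The primary endpoint is untouched.

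The size is a rough ceiling of 11 of 108 subjects, about 5 per arm. It should not be read as an expected loss. The 10% includes hospital-environment events, its follow-up window is not given, and some infections or healing complications would arise after participation ends. The ceiling holds only if the 10% applies to this population, and it counts qualifying subjects only; training and replaced subjects are additional. No direction of bias can be claimed.

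**What to change.** Reconcile 12.3.1 with 10.6, 10.11, 12.1, 12.2.1 and 12.2.2. Delete the non-capture clause, or narrow it, so that every AE in the collection window, and at minimum every SAE and death, is recorded regardless of attribution and relatedness is assigned afterwards. The window should be stated once, since 10.11 and 12.1 describe it differently and 10.9.7 and SAP 7.10 refer to sensor application through removal.

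If workload is the reason for the clause, replace it with a pre-listed set of expected non-serious event types that need no AE form. The exemption should be defined by event type and not by a causality call. Section 12.3.4 already does something similar for mild, short-lived skin reactions. Separate relatedness fields for device, anesthetic management and surgery would help interpretation but are optional.

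The cost is a wording amendment, a few more AE forms (on the ceiling above, about 11 subjects with at least one event), and a somewhat higher reported AE rate.
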